5.4.3 End of Study

Once the subject is seen for the final visit at 12 months post-surgery, the subject will have completed the study. This will be documented on a study completion form.

5.4.4 Subject Replacement Procedures

Subjects that are considered screen failures will be replaced.

Subjects that have been randomized, have scaling and root planing with Emdogain® treatment during Visit 2 are considered enrolled and will not be replaced.

5.4.5 Protocol Deviations

Deviations from the procedures established in the protocol are not permitted. If a deviation occurs, the deviation will be recorded on the Protocol Deviation Log. The sponsor shall be notified immediately of any deviations in informed consent and

inclusion/exclusion criteria (i.e. major deviations), and the IRB shall be notified according to the requirements of the local IRB.

Any deviation from the protocol (including deviations from the expected study visit windows, i.e. minor deviations) may jeopardize the study outcome. Non-compliance of the subjects, as well as of the Investigators, may lead to the closure of the respective study center.

6 Schedule of Assessments

An overview of the schedule of assessments is provided in the Table 1 - "Schedule of Assessments".

6.1 Visit Windows

Subjects need to be seen within the following windows:

Visit #	Visit Name	Visit Window
Visit 1	Informed Consent/Screening & Baseline Visit	14 - 0 Days before enrollment
Visit 2	Final Screening Randomization Minimally Invasive Scaling and Root Planing and Emdogain® First Application	RANDOMIZATION AND SURGERY - Point of enrollment Day 0
Visit 3	Supragingival Plaque Removal and Emdogain® Second Application	2-3 Weeks \pm 2-3 Days
Visit 4	Regular Periodontal Maintenance	1 Month \pm 1 Week
Visit 5	3-Month Follow-up Visit	3 Months \pm 1 Week
Visit 6	6-Month Follow-up Visit	6 Months \pm 2 Weeks
Visit 7	9-Month Follow-up Visit	9 Months \pm 2 Weeks
Visit 8	12-Month Follow-up Visit	12 Months \pm 2 Weeks

6.2 Visit 1 – Screening & Baseline Visit

This visit should be completed within 14 days prior to the Surgery Visit (Visit 2). An initial evaluation will be conducted to determine whether the subject meets the study inclusion and exclusion criteria.

The following procedures and assessments will be performed and recorded at the screening visit:

- Informed consent
- Medical & Dental history

- Demographics
- Pregnancy Test
- Inclusion/exclusion criteria
- Initial Periodontal Examination and Assessment of Periodontal Status
- Collection of baseline clinical measurements:
 - Pocket Probing Depth
 - Gingival Margin
 - Bleeding on Probing
 - Full Mouth Plaque Score
- Radiographs
- Photographs
- Concomitant Medications
- Adverse Events check

6.3 Visit 2 – Minimally Invasive Scaling and Root Planing and Emdogain® First Application (SURGERY)

Visit 2 needs to be completed within 14 days from the Screening & Baseline Visit. It is possible to conduct Visit 1 and Visit 2 at the same office visit.

The following will be conducted during this visit:

- Final review of inclusion/exclusion criteria and determination of subject eligibility.
- Identification of the contralateral quadrants and treatment assignment
- Root Dentin Hypersensitivity at the study teeth
- Randomization (if subject meets all eligibility criteria).
- Minimally invasive scaling and root planing, control of bleeding, application of PrefGel®, irrigation with sterile saline, and first application of Emdogain® for teeth treated in test quadrant.
- Scaling and root planing and control of bleeding for teeth treated in control quadrant.
- Pain scale completion by the patient

- Post treatment oral hygiene instructions
- Photographs
- Concomitant Medications
- Adverse Events check

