5.2.1 Selection and Assignment of Quadrants

The inclusion and exclusion criteria will be reviewed (Section 3.7.1 and 3.7.2). If the subject remains eligible, randomized treatment assignment of a quadrant (test or control), will be done via randomization envelopes. At Visit 2, the Investigator or designee will open a sealed randomization envelope. The randomization envelope will identify the treatment assignment for the right and left quadrants, both in the same arch of the eligible patient. **Randomization envelopes must be open in sequential order.**

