5.2.2 Surgery - Minimally Invasive Scaling and Root Planing and Emdogain® First Application

Patients that have been randomized and have scaling and root planing with Emdogain® treatment during Visit 2 are considered enrolled in the study. Each subject will receive local anesthetic and be treated in one visit with a sequence of steps defined by the treatment assignment:

- Test treatment: For the quadrant assigned to scaling and root planing + Emdogain® the following steps should be conducted for treatment: scaling and root planing, control of bleeding, application of PrefGel® (until there is clear overflow from the pocket) to remove any residual smear layer for 2 minutes, irrigation with sterile saline thoroughly, and application of Emdogain® starting apically and advancing coronally until there is clear overflow from the pocket.

- Control treatment: For the contralateral quadrant, assigned to scaling and root planing alone, the following steps should be conducted at the same visit as the test treatment: scaling and root planing and control of bleeding.

Mechanical debridement will be carried out in the manner commonly performed by the clinician (e.g., hand instrumentation, ultrasonic scalers with diamond tips). No antimicrobial agents or techniques (antibiotics or antiseptics, photodynamic therapy) will be applied during treatment. No vasoconstrictors (other than 1:100 000 or 1:200 000 epi in local anesthetic) or hemostatic agents will be used in surrounding soft tissues or pockets. Bleeding will be stopped by conventional techniques as much as possible. No sutures or periodontal dressings will be applied.

In order to standardize treatment across centers, only loupes or a microscope can be used as an assistive visual aid for debridement and removal of calculus from defects.

Other quadrants not being evaluated in the study should be treated according to standard practice.

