8.2.1 Baseline Characteristics

The baseline data are presented on the basis of all screened subjects. They are collected at the Visit 1 and include: Medical & Dental History, Demographics, Inclusion & Exclusion Criteria, Concomitant Medications, Adverse Event Check, PPD, GM, CAL, FMPS, and Pain (see details in Section 5.1 and 5.3).

To assess balance in baseline characteristics, the distribution of each baseline variable of interest will be compared between the two treatment groups, i.e. test and control quadrants of the same arch. Continuous variables will be summarized using mean, median, standard deviation, 95% confidence interval, and range; testing between the two groups will be based on a two-sample t-test (or Wilcoxon rank-sum test as appropriate). Categorical variables will be summarized using counts and percentages, and differences between treatment groups will be assessed using a Chi-square test (or Fisher's exact test as appropriate).

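### Section 6.3 places allocation both before and after the only baseline hypersensitivity test, so that baseline can be graded with the allocation known

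*Combined protocol and SAP*

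**What the plan says.** Section 6.3 introduces the Visit 2 list with "The following will be conducted during this visit". The first bullet is the final eligibility review. The next three, in order, are:

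- "Identification of the contralateral quadrants and treatment assignment"
- "Root Dentin Hypersensitivity at the study teeth"
- "Randomization (if subject meets all eligibility criteria" (closing the parenthesis)

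Section 5.2.1 describes how allocation is made. Once the criteria have been reviewed and the subject remains eligible, "randomized treatment assignment of a quadrant (test or control), will be done via randomization envelopes". It continues: "At Visit 2, the Investigator or designee will open a sealed randomization envelope". The envelope gives the treatment for the right and left quadrants.

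Section 5.3.7 defines the test as a three-second air blast on the study tooth, graded none, mild, moderate or severe from the subject's response. It is done at Visit 2 and then from month 3 onward, with no Visit 1 measurement. Section 5.3 has the same examiner take all measurements throughout. The text states no masking of the examiner or the subject.

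Change in hypersensitivity is a secondary endpoint (3.4.2) and an additional endpoint at 3, 6 and 9 months (3.4.3). Section 4.6 names a decrease in it as an anticipated benefit. Section 8.3.2 plans percentages by treatment group. The synopsis adds raw values and change from baseline for the endpoints.

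**The concern.** A change score is only as sound as its baseline. Probing depth, gingival margin, bleeding and plaque all have their baseline at Visit 1, before allocation. Hypersensitivity is the exception: its single baseline is taken at the visit where the envelope is opened, and section 6.3 mentions allocation on both sides of it.

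The grade combines the subject's reaction with the examiner's judgment of it. If either knows which quadrant will receive the device, the two sides may be graded differently. Because one baseline serves every later visit, such a difference would carry into the change at 3, 6, 9 and 12 months.

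**Working it through.** The plan gives no figure to reproduce, so the check compares the sections and then follows a baseline error through the change score.

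**1. One act or two?** In 5.2.1 the quadrant's treatment is assigned by opening the envelope, and opening the envelope is the randomization. No other assignment step is described. The second and fourth bullets of 6.3 therefore name the same act, with the third bullet, the test, between them.

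**2. Which orders comply?**

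| Followed by the site | Order | Allocation known at baseline grading? |
|---|---|---|
| 5.2.1 and second bullet of 6.3 | eligibility review, envelope, test | Yes |
| Fourth bullet of 6.3 | eligibility review, test, envelope | No |

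Both orders fit the text. Section 5.2.1 goes straight from eligibility review to envelope, which matches the first two bullets. Nothing in 5.2.1, 5.3.7 or 6.3 requires the test to be finished before the envelope is opened.

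**3. Does anything else prevent it?** The investigator or a designee opens the envelope (5.2.1), and one examiner measures throughout (5.3). The documents do not say whether these are the same person or different people, and they state no masking.

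**4. How would a baseline error act?** Score the grades 0 to 3 for illustration. Let e_T and e_C be the grading errors at baseline on the test and control sides, and b = e_T − e_C. Change is follow-up minus baseline, so the test-minus-control difference in recorded change equals the true difference minus b. If b = 0, the errors cancel. If b > 0, the test side appears to improve more; if b < 0, a real improvement is hidden. The same b enters at every follow-up visit.

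**5. How much could it matter?** The documents give neither b nor a standard deviation. As an illustration only, assume:

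- n = 42 completers, from 50 × (1 − 0.15) = 42.5 (section 8.1), rounded down;
- a standard deviation (SD) of the within-subject difference in change of 0.5 to 1.0 grade;
- a two-sided 5% paired z-test with no true effect.

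Then SE = SD/√42, which is 0.077 for SD 0.5 and 0.154 for SD 1.0. The rejection probability is Φ(b/SE − 1.96) + Φ(−b/SE − 1.96).

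| b (grades) | SD 0.5 | SD 0.75 | SD 1.0 |
|---|---|---|---|
| 0 | 5.0% | 5.0% | 5.0% |
| 0.1 | 25.4% | 13.9% | 9.9% |
| 0.2 | 73.6% | 40.8% | 25.4% |
| 0.3 | 97.3% | 73.6% | 49.4% |

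The table shows sensitivity to an assumed b and does not estimate what happened. The supplied text specifies no test for this endpoint.

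**The case against.** The strongest reply is that 6.3 is a checklist rather than a sequence. Its opening words say only what is done at the visit. The list also contains an item that cannot be in time order: pain scale completion stands before hygiene instructions and photographs, although the scale is first completed at home one to two days later. If the list is read as a sequence, the bullet actually named randomization follows the test, and the baseline is graded before allocation.

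This shows that the protocol can be followed without any problem, so bias cannot be asserted. It does not remove the contradiction. Section 5.2.1 gives its own order, from eligibility review to envelope, and a site following it with the second bullet would open the envelope first. Section 8.3 pools four centers on the strength of standardized procedures, and two permitted orders do not meet that standard.

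A reader might also draw four stronger inferences, which the documents do not support:

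- **Table 1 confirms the order.** Its rows are not chronological. The quadrant identification row, marked at Visit 2, sits above measures whose baseline is at Visit 1.
- **The test may be done under anesthesia.** Section 5.2.2 says "Each subject will receive local anesthetic and be treated in one visit", which ties the anesthetic to the surgical step. Both study quadrants are treated at that visit, so no difference between sides follows.
- **A distorted baseline would go unseen because 8.2.1 omits this measure.** That list, which includes "Adverse Event Check, PPD, GM, CAL, FMPS, and Pain", describes data collected at Visit 1, and this test is at Visit 2. The synopsis promises raw values, and section 8.2 names hypersensitivity among the categorical data summarized in each treatment group.
- **A particular share of teeth would be graded too high on the test side.** No document supports such a share or its direction.

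**Conclusion.** The point holds as a contradiction in a stated procedure. The protocol places a single act both before and after the only baseline for a listed secondary endpoint, and it contains no ordering or masking rule that settles the matter. The endpoint is open to bias of unknown size and direction. A reader might infer that the endpoint is biased, but that would require the envelope to have been opened first and the two sides to have been graded differently, and the documents establish neither.

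The conclusion rests on reading 5.2.1 as making assignment and randomization the same act, and on the absence of any masking statement in the supplied text. How far a baseline error reaches the reported result depends on the analysis of change. Section 8.3.2 specifies only percentages by group, and the protocol defers testing to the SAP.

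The reach is limited. This is one secondary endpoint in a study that section 8.1 calls a pilot. The primary endpoint is derived from probing depth and gingival margin, both first recorded at Visit 1, and is not affected. Still, the correction is almost free and removes an avoidable opening for bias, so it should be made.

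**What to change.** 1. Delete treatment assignment from the second bullet of 6.3, leaving identification of the contralateral quadrants, so that allocation appears once, after the test.
2. State in 6.3 and 5.3.7 that baseline hypersensitivity is completed and recorded before the randomization envelope is opened.

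Alternatively, record it at Visit 1 with the other baseline measures and move its mark in Table 1 accordingly. Section 6.3 allows Visits 1 and 2 on the same occasion, so the sentence about the envelope is worth having in either case.

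The cost is two short text edits, with the same test and no added burden. The synopsis planned enrollment through December 2016; if it has closed, ask each center which order it followed and report the answer with this endpoint.

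The change protects the baseline only. Grading at 3, 6, 9 and 12 months also has no stated masking, and that needs separate attention.

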6.4 Visit 3 - Supragingival Plaque Removal and Emdogain® Second Application

The patient will be recalled for a visit at 2-3 weeks after the surgery, for a periodontal cleaning with supragingival plaque removal and reapplication of Emdogain® according to the treatment assignment.

In particular, the subject will have the following procedures and/or evaluations performed and documented:

- Supragingival plaque removal for both test and control quadrants
- Emdogain® re-application to teeth treated in test quadrant (no PrefGel® re-application)
- Full Mouth Plaque Score
- Pain scale completion by the patient
- Post treatment oral hygiene instructions
- Photographs
- Concomitant Medications
- Adverse Events check

6.5 Visit 4 – Periodontal Maintenance

The subject will be recalled for a visit at 1 month after Surgery.

In particular, the subject will have the following procedures and/or evaluations performed and documented:

- Supragingival Prophylaxis.
- Photographs
- Concomitant Medications
- Adverse Events check

6.6 Visit 5 – Follow-up Visit 3 Months

Subjects will be recalled at 3 months after Surgery.

The subject will have the following procedures and/or evaluations performed and documented:

- Data Collection including: Pocket Probing Depth, Gingival Margin, Bleeding on Probing, Root Dentin Hypersensitivity at the study teeth
- Regular Periodontal Maintenance
- Photographs
- Concomitant Medications
- Adverse Events check

6.7 Visit 6 – Follow-up Visit 6 Months

Subjects will be recalled at 6 months after Surgery.

The subject will have the following procedures and/or evaluations performed and documented:

- Data Collection including: Pocket Probing Depth, Gingival Margin, Bleeding on Probing, Root Dentin Hypersensitivity at the study teeth
- Regular Periodontal Maintenance
- Photographs
- Concomitant Medications
- Adverse Events check

6.8 Visit 7 – Follow-up Visit 9 Months

Subjects will be recalled at 9 months after Surgery.

The subject will have the following procedures and/or evaluations performed and documented:

- Data Collection including: Pocket Probing Depth, Gingival Margin, Bleeding on Probing, Root Dentin Hypersensitivity at the study teeth
- Regular Periodontal Maintenance
- Photographs

- Concomitant Medications
- Adverse Events check

6.9 Visit 8 – Follow-up Visit 12 Months / Study End

Subjects will be recalled at 12 months after Surgery.

The subject will have the following procedures and/or evaluations performed and documented:

- Data Collection including: Pocket Probing Depth, Gingival Margin, Bleeding on Probing, Root Dentin Hypersensitivity at the study teeth, with addition of Full Mouth Plaque Score (FMPS)
- Regular Periodontal Maintenance
- Radiographs
- Photographs
- Concomitant Medications
- Adverse Events check

7 Evaluation of Adverse Events

For the avoidance of doubt, **all** AE/SAEs as defined below should be collected for all subjects from the time of screening (Visit 1).

7.1 Definitions

7.1.1 Adverse Event (AE)

An AE is defined as any untoward medical occurrence, unintended disease or injury, or any untoward clinical signs (including abnormal laboratory findings) in subjects, users or other persons, whether or not related to the investigational medical device. This definition includes events related to the investigational medical device or the comparator, or events related to the procedures involved. For users or other persons, this definition is restricted to events related to investigational medical devices.

7.1.2 Serious Adverse Event (SAE)

Any adverse event that:

- led to a death
- led to a serious deterioration in the health of the subject, that either resulted in

- a life-threatening illness or injury, or
 - a permanent impairment of a body structure or a body function, or
 - in-patient or prolonged hospitalization, or
 - medical or surgical intervention to prevent life-threatening illness or injury or permanent impairment to a body structure or a body function,
- led to fetal distress, fetal death, or a congenital abnormality or birth defect

A planned hospitalization for a pre-existing condition, or a procedure required by the protocol, without serious deterioration in health, is not considered to be a serious adverse event.

7.1.3 Device Deficiency (DD)

A device deficiency is an inadequacy of a medical device with respect to its identity, quality, durability, reliability, safety or performance. Device deficiencies include malfunctions, use errors and inadequate labeling.

7.1.4 Adverse Device Effect (ADE)

An ADE is an adverse event related to the use of an investigational medical device. This definition includes adverse events resulting from insufficient or inadequate instructions for use, deployment, implantation, installation, or operation, or any malfunction of the investigational medical device. This definition includes any event resulting from use error or from intentional misuse of the investigational medical device. ***Any adverse event which the clinical investigator believes has even a possible relationship to the device, the event will be classified as and ADE.***

7.1.5 Serious Adverse Device Effect (SADE)

An SADE is an adverse device effect that has resulted in any of the consequences characteristic of a serious adverse event.

7.1.6 Unanticipated Serious Adverse Device Effect (USADE)

An USADE is a serious adverse device effect which by its nature, incidence, severity or outcome has not been identified in the current version of the risk analysis report.

7.1.7 Anticipated Serious Adverse Device Effect (ASADE)

An ASADE is a serious adverse device effect which by its nature, incidence, severity or outcome has been identified in the risk analysis report.

Summary of the classification for adverse events:

Adverse events	Non-device related	Device or procedure related	
Non-serious	Adverse Event (AE)	Adverse Device Effect (ADE)	
Serious	Serious Adverse Event (SAE)	Serious Adverse Device Effect (SADE)	
		Anticipated Anticipated Serious Adverse Device Effect (ASADE)	Unanticipated Unanticipated Serious Adverse Device Effect (USADE)

7.2 Assessment of Adverse Events

In the event of an adverse event, the Investigator or another suitably qualified clinician who is trained in recording and reporting AEs and have been delegated to this role (such delegation must be captured in the study site delegation log) must review all documentation (e.g., hospital notes, laboratory and diagnostic reports) relevant to the event.

Each adverse event should be assessed for seriousness, relationship to the study device or the procedure, severity and expectedness, as described below, by the Investigator.

7.2.1 Seriousness

An adverse event will be described as serious if it meets the definition in Section 7.1.2. The rationale for the assessment shall be provided in a short narrative.

7.2.2 Relationship to the Study Device

The Investigator should assess the relationship of the adverse event to the study product and study procedure. The relationship should be assessed using the following categories:

- **Definitely Related** – There is a reasonable causal and temporal relationship between the treatment with the study device and the adverse event.
- **Possibly Related** – The relationship between the treatment with the study device and the adverse event is less likely; however, the determination that there is no relationship cannot be made.
- **Not related** – No relationship between treatment with the study device and the adverse event is obvious

NOTE: Device deficiencies that might have led to an SAE are always related to the medical device.

The Investigator shall provide rationale for the assessment of the expectedness in a short narrative on the AE/ADE Report Form.

7.2.3 Relationship to the Procedure

The Investigator should assess the relationship of the adverse event to the surgical procedure (i.e. application or reapplication of Emdogain®). The relationship should be assessed using the categories described in Section 7.2.2.

The Investigator shall provide rationale for the assessment of the expectedness in a short narrative on the AE/ADE Report Form.

